(Visit 3) Outpatient treatment 2: IVIG 1 gram/kg over 1 day (to be administered 21±3 days after completion of initial treatment).

Placebo would include administration of 0.1% albumin per day over 1 day.

Selection of Placebo: The inclusion of placebo is critically important in a pilot study of this type in order to understand the potential treatment effects of IVIG on disease. Low dose albumin has been selected as the choice of placebo based on standard dosing from several other clinical trials of IVIG in different forms of neuropathy.

OBJECTIVES (Succinctly describe the major objectives for the overall proposed project)

To develop a therapeutic intervention for treatment induced neuropathy in diabetes. The primary endpoint will be to improve the pain associated with TIND, as well as improve nerve fiber structure (measured by biopsy analysis of IENFD) and by improvement in nerve fiber function.

Finally, we will improve our understanding of the potential mechanisms underlying this disorder, and define a potential plasma biomarker (elevated cytokines and inflammatory markers) that could identify patients that would respond to the treatment.

Primary endpoint:

The change in neuropathic pain severity and distribution between treatment and placebo groups between visit 1 and visit 2.

We expect that individuals with TIND treated with IVIG will have a >50% reduction in neuropathic pain and >30% reduction in the distribution of neuropathic pain 6 weeks after treatment. We expect that placebo that will have <20% reduction in neuropathic pain and no change in the distribution of neuropathic pain 6 weeks after treatment.

Secondary Outcomes:

The difference in quantified neurologic examination scores, biopsy scores and autonomic function between treatment and placebo groups at 6 weeks and 12 weeks.

We expect that individuals with TIND treated with IVIG will have improvements in quantified neurologic examination scores, autonomic function testing and nerve fiber density at follow up visits 4 and 5 compared to their initial visit. We expect that placebo treated individuals will have either no change or worsening of quantified neurologic examination scores, autonomic function testing and nerve fiber density at follow up visits 4 and 5 compared to their initial visit.

Exploratory Outcomes:

Exploratory outcome measures will include the effects of cytokine on neuropathic pain, small fiber neuropathy and autonomic neuropathy (heart rate variability).

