Statistical Analysis Plan

Power calculations:

This pilot study is being conducted in order to obtain adequate preliminary data for a larger clinical trial, but is powered to answer the primary endpoint analysis. Secondary endpoints and exploratory endpoints are not included in the power analysis

Group	Change in pain score	Change in IENFD
Placebo	2+/-2	0.5+/-1
IVIG	5+/-3	3+/-1.9

Number of pairs needed for 80% power to detect change.	10	7
---	-----------	----------

Change in pain score calculation: We are planning a study of a continuous response variable from matched pairs of study subjects. Prior data indicate that the difference in the pain response of matched pairs is normally distributed with standard deviation 3. If the true difference in the mean response of matched pairs is 3, we will need to study 10 pairs of subjects to be able to reject the null hypothesis that this response difference is zero with probability (power) 0.8. The Type I error probability associated with this test of this null hypothesis is 0.05.

Change in IENFD score calculation: We are planning a study of a continuous response variable from matched pairs of study subjects. Prior data indicate that the difference in the response of matched pairs is normally distributed with standard deviation 1.9. If the true difference in the mean response of matched pairs is 2.5, we will need to study 7 pairs of subjects to be able to reject the null hypothesis that this response difference is zero with probability (power) 0.8. The Type I error probability associated with this test of this null hypothesis is 0.05.

Based on our preliminary data from the 4 subjects treated with IVIG, and the 104 untreated subjects with TIND, and the power analysis listed in Table 3, we calculate that 10 subjects in each of the treatment and placebo treated arms will provide >80% power with a 2 sided alpha of 0.05 to detect a difference between placebo and active treatment groups.

A total of 20 subjects will be included in this study:

- 1) IVIG treatment: Individuals with poorly controlled diabetes that have a sudden improvement in their HbA1C and the development of neuropathy (*meeting criteria for treatment induced neuropathy*). Subject number =10
- 2) Placebo Treatment: Individuals with poorly controlled diabetes that have a sudden improvement in their HbA1C and the development of neuropathy (*meeting criteria for treatment induced neuropathy*). Subject number =10.

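### The power claim covers a primary endpoint of pain severity and distribution, but no SD, scale or calculation supports it for distribution, and no rule says how the two components combine

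*Combined protocol and SAP*

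**What the plan says.** All references are to the combined protocol and SAP.

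- **Primary endpoint:** "The change in neuropathic pain severity and distribution between treatment and placebo groups". One endpoint is named, with two components. Each has its own expected result. For distribution the plan expects ">30% reduction in the distribution of neuropathic pain 6 weeks after treatment" on IVIG and "no change in the distribution of neuropathic pain 6 weeks after treatment" on placebo.
- **Statistical Analysis Plan, Power calculations:** the study is a pilot "but is powered to answer the primary endpoint analysis". The only exemption is "Secondary endpoints and exploratory endpoints are not included in the power analysis". Distribution is neither secondary nor exploratory, so the claim extends to it.
- **Power table and worked calculations:** there are two columns, pain score and IENFD, and one paragraph for each. The pain paragraph opens "Change in pain score calculation: We are planning a study of a continuous response variable" and states that "the difference in the pain response of matched pairs is normally distributed with standard deviation 3". Biopsy results are listed under Secondary Outcomes, yet IENFD receives a calculation and distribution does not.
- **Conclusion of the power section:** 10 subjects per arm are said to give over 80% power at a two-sided alpha of 0.05.

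**The concern.** The plan claims a property (over 80% power at 5% two-sided error) for an endpoint with two components and does the arithmetic for one. The text gives no decision rule for the pair and no division of alpha.

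Two things are at stake. A null result on distribution could be read as coming from an adequately powered comparison when the plan gives no basis for that. And the stated power and alpha cannot both describe the endpoint as written until the combination rule is fixed, because requiring both components affects power and accepting either affects type I error. Since the pilot is meant to supply the figures for a larger trial, a misread distribution result would carry into that design.

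**Working it through.** **1. The plan's own figures.** Paired t-test, noncentrality (difference / SD) × √n, n − 1 degrees of freedom, two-sided 0.05.

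- Pain: difference 3, SD 3, n = 10 gives noncentrality 1 × √10 = 3.16 and power 0.803. With 9 pairs power is 0.748. The stated 10 pairs are reproduced.
- IENFD: difference 2.5, SD 1.9, n = 7 gives power 0.825. The stated 7 pairs are reproduced.
- Distribution: there is no stated figure to reproduce.

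**2. What is available for distribution.**

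| Input | Given? | Where |
|---|---|---|
| Expected effect | Yes: >30% reduction vs no change | Primary endpoint |
| N per arm, alpha | Yes: 10; 0.05 two-sided | Power calculations |
| Measurement scale | No | – |
| SD of change | No | – |
| Calculation | No | – |

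**3. Range of power for distribution.** Assumptions: the effect is a difference of 30 percentage points in mean change (30 minus 0), the SD is the same in both arms, and the test is a two-sample t-test with 10 per arm (18 degrees of freedom, two-sided 0.05). The noncentrality is (30 / SD) × √(10/2).

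| Assumed SD (points) | Noncentrality | Power | N per arm for 80% |
|---|---|---|---|
| 15 | 4.47 | 0.99 | 6 |
| 20 | 3.35 | 0.89 | 9 |
| 25 | 2.68 | 0.72 | 12 |
| 30 | 2.24 | 0.56 | 17 |
| 40 | 1.68 | 0.36 | 29 |

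Power of 80% needs a standardised difference of 1.325, so the SD must be no more than 30 / 1.325 = 22.6 points. Under the plan's matched-pairs formula, 10 pairs reach 0.803 when the SD of pair differences is 30 points (30/30 = 1, as for pain).

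**4. Severity as a two-arm comparison.** The trial randomizes to two parallel arms. With the table SDs of 2 and 3, the pooled SD is √((4 + 9)/2) = 2.55. With a difference of 3 and 10 per arm, power is 0.70 (Welch test by simulation 0.69), and 13 per arm are needed for 80%. With SD 3 in both arms, power is 0.56.

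**5. The missing combination rule.**

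- *Both must succeed.* The probability that both succeed cannot exceed the probability that severity succeeds. The ceiling is therefore 0.803 on the plan's paired figure, or 0.70 on the two-sample figure. As an illustration with distribution SD 20 and independent components, the results are 0.803 × 0.887 = 0.71 and 0.702 × 0.887 = 0.62.
- *Either suffices, each tested at 0.05.* With independent components, type I error is 1 − 0.95² = 0.0975. Simulation of the two-sample tests gives about 0.10, 0.09 and 0.08 at correlations of 0, 0.5 and 0.8.

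**The case against.** The strongest reply has four parts.

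*Distribution is not without inputs.* A reader might infer that it has none at all. That is wrong: an expected effect, the number per arm and alpha are all stated. What is missing is the scale, the SD and a calculation. This stands, and the point is worded accordingly.

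*Low power is not demonstrated.* A reader might infer that the claim fails for distribution. The documents do not show this. At an SD of 15 or 20, power is 0.99 or 0.89, and nothing in the plan favours a larger SD. The plan also expects more than 30%, so 30 points is the low end of its own expectation. This stands: the claim is unsupported, not refuted.

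*A low joint power should not be charged to this gap alone.* With distribution SD 30 and the table inputs for severity, joint power is about 0.40 to 0.51 over correlations of 0 to 0.8. Much of that shortfall comes from severity's own two-sample power of 0.70, which reflects the matched-pairs calculation, a separate matter. This also stands; only the ceiling in step 5 is relied on here. Conversely, nobody should infer that severity is adequately powered as planned.

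*It is a pilot.* That limits the consequences of a misread null. It does not remove the problem, because the power section acknowledges pilot status and then claims power for the primary endpoint regardless.

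**Conclusion.** The concern holds in a limited form. The claim of power for the primary endpoint has no support for pain distribution, one of the two components the Primary endpoint section names. Whether power there is above or below 80% cannot be settled from the documents: it depends on whether the SD is below or above about 22.6 points, under the assumptions of a 30-point difference, equal SDs and a two-sample t-test.

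The missing combination rule matters whatever that SD is. If both components are required, power is at most severity's 0.803 (paired) or 0.70 (two-sample), so over 80% is attainable only on the paired figure and only if distribution almost always succeeds when severity does. If either is enough, type I error is about 8% to 10% for correlations from 0.8 down to 0, not 5%. The stated pairing of over 80% power with 5% error is therefore not established for the endpoint as defined. This should be corrected, but it is a fault in what the plan claims and does not affect the data to be collected.

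**What to change.** 1. **Primary endpoint section:** make change in pain severity the single primary endpoint, tested at two-sided 0.05.
2. **Secondary Outcomes:** list change in pain distribution first, reported as an estimate with a 95% confidence interval and no power claim. State the measure and scale, since the visit procedures name only pain VAS scores and pain questionnaires.
3. **Objectives:** align the sentence that also places IENFD and nerve fiber function under the primary endpoint. Otherwise the text will still name several primaries.
4. **Power calculations:** limit the power statement to pain severity and give its figure for the two-arm comparison, about 70% with the table SDs of 2 and 3 and 10 per arm. Keeping the over-80% figure while narrowing the claim would leave a statement that the two-arm design does not meet.

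If the sponsor prefers to keep distribution primary, the alternative is to supply its scale, SD and a two-sample calculation, and to state whether both components must succeed or either suffices, with alpha split in the latter case.

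Cost: a few sentences of wording, with no added patients or procedures. The downside is that distribution loses primary status and the stated power becomes less favourable.

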Study Title “The Efficacy Of Intravenous Immunoglobulin Therapy
In Treatment Induced Neuropathy Of Diabetes”

NCT number: NCT02915263

Version 2.0

Document Date: Revised 11/10/2016 (Original 9/10/2016)

Protocol:

This study will be a double-blind, placebo-controlled pilot study of the effects of immune globulin (IVIG) on treatment induced neuropathy in diabetes. The goal of this pilot study is to obtain preliminary data on the magnitude of the treatment effect of IVIG on the neuropathic pain and neuropathy severity associated with TIND. The preliminary data will be used to power a larger treatment trial, and to aid our understanding of the mitigating factors in the treatment response.

The study will include a total 20 individuals. Subjects will be randomized equally to treatment or placebo. Treatment will consist of IVIG administered at 2 grams/kg divided over 2-4 days, with a follow up treatment 3 weeks (+/-3 days) later of IVIG 1gram/kg administered over 1 day.

Subjects: All individuals participating in the study will be recruited from Joslin Diabetes Center or Beth Israel Deaconess Medical Center from the clinical practice of [name]. Recruited subjects will review and sign the informed consent, undergo screening for eligibility:

Inclusion Criteria:

- Individuals with a diagnosis of diabetes and treatment induced neuropathy (defined by the onset of neuropathic pain within 8 weeks of a change in HbA1C exceeding 3 points over 3 months).
- Ages 18-60.
-

Exclusion Criteria:

- No other known cause of neuropathy (chemotherapy, toxins, other medical disorder).
- Anticoagulation with warfarin, aspirin & Plavix together, or other anticoagulant that would place subjects at undue risk of bleeding from a skin biopsy. Aspirin or Plavix alone are not an exclusion criteria.
- Evidence of severe vascular disease (history of ulceration, poor wound healing, vascular claudication)
- Clinically active coronary artery or cerebrovascular disease
- History of allergic reaction to local anesthesia for skin biopsies or history of scarring or keloid formation.
- History of reaction to blood products or immune globulin.

Screening Visit (Visit 1): Protocol Procedures- After signing an informed consent subjects will undergo the following:

- 1) Undergo a general physical examination, Pain VAS scores, pain questionnaires and SF-36.
- 2) Have a quantified neurological (neuropathy) examination using the Utah Early Neuropathy Score (UENS)(Singleton *et al.*, 2008).

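### The pain sample size uses a matched-pairs formula for an unmatched two-arm trial; with the plan's tabulated SDs, 10 per arm gives about 70% power, not >80%.

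*Combined protocol and SAP*

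**What the plan says.** The Protocol section describes a two-arm design: "Subjects will be randomized equally to treatment or placebo". The Primary endpoint paragraph compares the change in pain between the treatment and placebo groups.

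The Power calculations section of the SAP states that the pilot "is powered to answer the primary endpoint analysis". Its table gives the change in pain score as 2+/-2 for placebo and 5+/-3 for IVIG, and the change in IENFD as 0.5+/-1 and 3+/-1.9. The +/- values are not labelled. A further row gives the number of pairs needed for 80% power: 10 for pain and 7 for IENFD.

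The accompanying text treats both endpoints as matched-pair comparisons. For pain, "Prior data indicate that the difference in the pain response of matched pairs is normally distributed with standard deviation 3", with a true mean difference of 3. For IENFD, "the difference in the response of matched pairs is normally distributed with standard deviation 1.9", with a true mean difference of 2.5. The source is given as follows: "Based on our preliminary data from the 4 subjects treated with IVIG, and the 104 untreated subjects with TIND". The section concludes that "10 subjects in each of the treatment and placebo treated arms will provide >80% power" at a two-sided alpha of 0.05.

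**The concern.** Ten matched pairs and two independent groups of ten are different designs. A paired calculation uses the SD of within-pair differences, and its gain comes from correlation within pairs. Nothing in the eligibility criteria, the randomisation sentence or the visit schedule creates pairs, and the prior data are 4 treated and 104 untreated subjects, which are not pairs either.

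The SDs entered for the paired difference, 3 and 1.9, equal the IVIG row's +/- values for both endpoints. This suggests, though only by inference, that one arm's SD was used as the SD of a difference.

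The SAP presents adequate power for the primary endpoint as a property of the trial. If it is wrong, a null pain result would be read as stronger evidence against an effect than it is. The Protocol section also says "The preliminary data will be used to power a larger treatment trial"; if the same formula were reused there, that trial would be undersized too.

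**Working it through.** **Inputs** (all from Power calculations): pain difference 5 − 2 = 3; pain SDs 2 and 3; IENFD difference 3 − 0.5 = 2.5; IENFD SDs 1 and 1.9; 10 per arm; two-sided alpha 0.05. Reading the +/- values as SDs is an assumption, supported by the SAP's own use of 3 and 1.9 as standard deviations.

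**1. Reproducing the plan's figures.** For a paired t-test, the noncentrality is (difference / SD of differences) × √n, with n − 1 degrees of freedom.

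- Pain: (3/3) × √10 = 3.16 on 9 df gives power 0.803. Nine pairs give 0.748, so the stated 10 pairs is reproduced.
- IENFD: (2.5/1.9) × √7 = 3.48 on 6 df gives power 0.825. Six pairs give 0.732, so the stated 7 pairs is reproduced.

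**2. What the table implies for a difference between two unmatched subjects.** The SD of the difference is √(SD₁² + SD₂² − 2ρ·SD₁·SD₂).

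- Pain, ρ = 0: √(4 + 9) = 3.61, not 3. An SD of 3 needs ρ = (4 + 9 − 9) / (2 × 2 × 3) = 0.33.
- IENFD, ρ = 0: √(1 + 3.61) = 2.15, not 1.9. An SD of 1.9 needs ρ = (1 + 3.61 − 3.61) / (2 × 1 × 1.9) = 0.26.

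**3. Power for the design described.** For two independent groups of 10, the standard error is √(SD₁²/10 + SD₂²/10), with 18 df for the pooled t-test.

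- Pain: standard error √(13/10) = 1.140; noncentrality 3/1.140 = 2.63.
- IENFD: standard error √(4.61/10) = 0.679; noncentrality 2.5/0.679 = 3.68.

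| Endpoint, 10 per arm | Pooled t | Welch | Normal approximation |
|---|---|---|---|
| Pain, difference 3, SDs 2 and 3 | 0.702 | 0.69 | 0.749 |
| IENFD, difference 2.5, SDs 1 and 1.9 | 0.936 | 0.927 | 0.957 |

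Simulation of the pain comparison (400,000 trials) gave 0.703 pooled and 0.691 Welch.

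**4. Scale of the pain shortfall.**

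- Difference detectable with 80% power at 10 per arm: 3.38 points (pooled t), 3.41 (Welch), 3.19 (normal approximation).
- With the placebo SD at 2, 80% power for 3 points requires an IVIG SD of 2.5 or less.
- For 3 points with SDs 2 and 3, the t-test gives 0.787 at 12 per arm and 0.821 at 13. The normal approximation reaches 80% at 12 (0.822).
- With SD 3 in both arms, power at 10 per arm would be 0.56, so 0.70 is not the harshest reading.

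**The case against.** The strongest objection is that the plan's inputs conflict, and one reading favours the plan. If the SD of 3 is taken literally as the SD of a difference between two independent subjects, the per-arm SD is 3/√2 = 2.12, and 10 per arm gives 84.8% power. That reading cannot be squared with the table, where SDs of 2 and 3 give a difference SD of 3.61. It also leaves unexplained why the entered SD equals the IVIG row's value for both endpoints.

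The documents do not strictly exclude pair-matched allocation, since they say little about randomisation beyond equal allocation. But the SAP mentions pairs only in the power text and names no matching factor, so unmatched arms are far the likelier reading. The authors can settle this in one sentence.

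Two caveats stand:

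- **The SDs are uncertain.** If the IVIG SD comes from the 4 treated subjects (an inference), its 95% interval on 3 df runs from about 1.7 to 11.2. With the placebo SD at 2, power then ranges from about 0.93 to 0.12. This is much wider than the effect of the formula, and it argues for showing a range, but it does not support a claim of >80%.
- **No analysis model is named.** Adjusting for baseline would give 0.74 if its correlation with the outcome were 0.3, and 0.82 if it were 0.5. Those correlations are assumed here, and the plan does not invoke them.

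One could also say that power matters little in a pilot meant to estimate an effect. That would carry weight if the SAP did not expressly claim power for the primary endpoint.

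**Conclusion.** The power statement for pain is wrong as written and must be corrected. The sample size rests on a matched-pairs formula that does not fit the unmatched parallel-group trial described. The mismatch itself does not depend on how the SD of 3 arose.

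Under a two-sided 0.05 t-test with a 3-point difference and SDs of 2 and 3, the stated power of >80% becomes about 70%. The risk of missing the assumed effect becomes about 30% rather than under 20%. The size of the shortfall depends on reading the table's +/- values as per-arm SDs and on an analysis unadjusted for baseline; the normal approximation (75%) also falls short of 80%. The error in formula affects both endpoints, but the shortfall is confined to pain.

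**What to change.** In Power calculations:

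- Delete the matched-pairs wording for both endpoints and the row giving the number of pairs.
- State that the comparison is between two independent randomised groups, and label the table's +/- values. If matching really is intended, the matching factors and procedure have to be described instead.
- Restate pain power for 10 per arm as about 70% for a 3-point difference with SDs 2 and 3, or equivalently 80% for about 3.4 points. A short range over plausible SDs would be useful, given the small number of treated subjects behind the inputs.
- Restate IENFD power for 10 per arm as about 94% for a difference of 2.5 with SDs 1 and 1.9.
- Bring the sentence claiming that the pilot is powered for its primary endpoint, and the closing >80% statement, into line with these figures.

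Keep N = 20; the 13 per arm above shows scale and is not a request. This changes SAP wording only, with no extra patients, visits or time. The one cost is a less favourable stated power for pain.

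### The claim of more than 80% power against placebo cites no placebo-treated data, has no margin if the 3-point difference is too large, and falls to about 70% for the two-arm comparison the trial will make

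*Combined protocol and SAP*

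**What the plan says.** All the planning figures are in the Statistical Analysis Plan, under Power calculations.

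- The table gives the change in pain score as 2+/-2 in the row labelled Placebo and 5+/-3 in the row labelled IVIG.
- The effect size is the gap between those means: "If the true difference in the mean response of matched pairs is 3". The SD used is that of a paired difference: "the difference in the pain response of matched pairs is normally distributed with standard deviation 3". From these, "we will need to study 10 pairs of subjects".
- The closing paragraph names the evidence: "Based on our preliminary data from the 4 subjects treated with IVIG, and the 104 untreated subjects with TIND". Together with the power table, this is said to show that 10 subjects per arm "will provide >80% power with a 2 sided alpha of 0.05 to detect a difference between placebo and active treatment groups".

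Elsewhere, the opening Protocol section describes a double-blind, placebo-controlled study in which "Subjects will be randomized equally to treatment or placebo". The control is an infusion of 0.1% albumin. The Selection of Placebo paragraph explains why a placebo is used: "The inclusion of placebo is critically important in a pilot study of this type in order to understand the potential treatment effects". The Primary endpoint paragraph expects a pain reduction above 50% on IVIG and below 20% on placebo, without giving a source for either.

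**The concern.** The power claim is about IVIG against placebo, but the only comparison subjects cited received no treatment. The endpoint is reported pain, which can respond to the experience of being infused. Blinded albumin recipients would share that response; untreated patients would not. If the Placebo row describes the untreated course, and the 4 IVIG-treated subjects knew what they were receiving, the gap of 3 points could be larger than the one this trial will see. The documents describe neither blinding nor a control for those 4 subjects.

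The SAP presents the study as powered for its primary endpoint, and its data are meant to power a larger trial. A power figure whose inputs have no stated source, and which does not fit the planned comparison, could mislead readers about what 20 subjects can show and could carry over into the next design.

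**Working it through.** **Inputs, all from Power calculations:** mean changes 2 and 5; SDs 2 and 3; planning difference 5 − 2 = 3; SD of paired differences 3; n = 10; two-sided alpha 0.05.

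**Step 1. Reproduce the stated figure.** For a paired t-test the noncentrality is (difference / SD) × √n = (3/3) × √10 = 3.162, with 9 df and critical value 2.262. Power is 80.3%; with 9 pairs it is 74.8%. The figure of 10 pairs is therefore right for its inputs, and 10 is the smallest number that reaches 80%.

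**Step 2. Keep the SAP's formula and change only the true difference.** The documents give no placebo-treated figure, so the range is an assumption: IVIG stays at 5, and the true albumin change is 2, 2.5, 3 or 3.5. This isolates the question of where the inputs come from.

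**Step 3. Use the comparison the trial will make.** With independent arms, SE = √(2²/10 + 3²/10) = √1.3 = 1.140, noncentrality = difference / 1.140, 18 df and critical value 2.101.

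| True difference | Paired noncentrality | Paired power, 10 pairs | Pairs for 80% | Two-sample noncentrality | Two-sample power, 10 per arm | Per arm for 80% |
|---|---|---|---|---|---|---|
| 3.0 | 3.162 | 80% | 10 | 2.631 | 70% | 13 |
| 2.5 | 2.635 | 65% | 14 | 2.193 | 55% | 18 |
| 2.0 | 2.108 | 47% | 20 | 1.754 | 38% | 27 |
| 1.5 | 1.581 | 29% | 34 | 1.316 | 24% | 47 |

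Reading down a power column shows the effect of a smaller true difference. Reading across from paired to two-sample power shows the effect of the formula. These are two separate issues: the fall from 80% to 70% at 3 points is due to the formula alone.

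In the two-sample setting, 80% power needs a true difference of 3.38 points. The expected 95% CI half-width is 2.101 × 1.140 = 2.40 points.

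**Step 4. Precision of the prior difference, only if the rows come from n = 4 and n = 104.** The documents do not confirm this.

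- Welch: SE = √(9/4 + 4/104) = 1.513, df 3.10, 95% CI −1.7 to 7.7.
- Pooled: SD = √((3×9 + 103×4)/106) = 2.035, SE = 2.035 × √(1/4 + 1/104) = 1.037, 95% CI 0.9 to 5.1.

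The two intervals disagree on whether zero is excluded. Pooling is doubtful here because the much smaller group has the larger SD.

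**The case against.** The strongest reply is that nothing ties the Placebo row to the untreated subjects. The closing paragraph lists the preliminary data and the power table side by side and does not match rows to sources. The row may be a planning assumption: on a 0–10 scale with baseline near 10 (the baseline is not given), changes of 2 and 5 would agree with the expected reductions of under 20% and over 50%. This stands. A reader might infer that the 3-point difference simply is IVIG against no treatment, or that planning left out any placebo response. The documents support neither. The row carries a 2-point change, and whether that is natural course, placebo response or both cannot be determined. Even as an assumption, though, the row has no cited placebo-treated data behind it, while the SAP attributes its figures to prior data.

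A second reply is that the 70% figure belongs to the matched-pairs problem. That is correct, which is why the two effects are shown separately above. The loss under the SAP's own formula does not depend on it.

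A third is that this is a pilot, and that small prior data, openly disclosed, are a usual reason to run one. That is fair, and it supports keeping N at 20. It does not support stating a power the design lacks. A reader might also infer that a null result would be taken as evidence against IVIG. The documents do not say so; the stated goal is preliminary data on the size of the effect.

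**Conclusion.** The concern holds in two parts.

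1. **Source of the inputs.** The power claim against placebo cites no placebo-treated data, and the origin of the Placebo row is not stated. If the true difference is below 3 points, the SAP's own formula gives 65%, 47% and 29% at 2.5, 2 and 1.5 points. That range is assumed. The direction is plausible if the row is the untreated course, but neither direction nor size can be fixed from the documents.
2. **Fit to the design.** Taking the table's means and SDs at face value, an unmatched two-sample comparison with 10 per arm has 70% power at 3 points, not more than 80%. This part needs no assumption about a placebo response, only that the arms are not matched; no matching is described.

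The intervals in Step 4 are conditional on unverified row sources and should carry little weight.

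**What to change.** Have the sponsor state the actual source of each row of the power table: which subjects, how many, and whether the figure was observed or assumed. The rows should not be relabelled as n = 104 and n = 4 unless the sponsor confirms it.

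Replace the sentence claiming more than 80% power with:

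> With 10 per arm and SDs of 2 and 3, a two-sample comparison has about 70% power for a true difference of 3 points against placebo, 55% for 2.5 and 38% for 2; 80% power requires a difference of about 3.4 points, and the expected 95% CI half-width is about 2.4 points.

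Keep N at 20. The cost is SAP wording only, with no more patients and no change to treatment. The downside is that the stated power becomes less favourable.
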